1.2 Data analysis

We will conduct a chi-square test of proportions analysis using Stata to compare arm 2 to arm 1 and arm 3 to arm 2 separately using intent-to-treat protocol for the ultrasound completion and any HCC surveillance imaging completion. As exploratory analyses, we will evaluate response by age, gender, race/ethnicity, income at the level of zip code, etiology of cirrhosis, and provider/specialty. We will also evaluate differences in response rate among MyPennMedicine users and non-users and scheduling modality (MyPennMedicine vs. call). Additionally, we will evaluate the percentage of HCC surveillance images that are abnormal, result in follow-up imaging, result in a diagnosis of HCC and follow-up care, and incidental findings during imaging between the study arms. Analysis will be conducted at least six months after initial outreach.

Study Design

[figure not shown]
1.1 Design

Randomized: This is a 3-arm randomized controlled trial. Patients with cirrhosis will be identified from eligible patients at the Penn Gastroenterology clinic via medical records query. Their providers will be contacted with the opportunity to opt-out on behalf of the patients. Approximately 490 eligible patients identified in the initial batch will be randomized 1:2:2 into a usual care arm and 2 intervention arms using a computer-generated randomization algorithm (Figure 1). Three months after the initial batch, approximately 110 newly eligible patients will be identified and randomized as described above (Figure 1). Three months after the second batch, a third and final data pull will be completed to identify any remaining patients meeting study criteria. Randomization will be stratified by batch. The research coordinator will record the randomization assignments on a master list which will be maintained on a password protected computer. The usual care arm (120 patients) will receive standard of care. The first intervention arm (240 patients) will involve facilitated outreach and opt-out framing, and research staff will send a letter to those patients encouraging them to get a surveillance ultrasound and include an order

slip for them to get it done at a health system facility. The second intervention arm (240 patients) will be the same process but will also offer an unconditional incentive of \$20 compensation.

Blinding: The investigators will be blinded to the randomization assignment. The research staff will be unblinded. The blinding may be broken for clinical care purposes.

Figure 1. Batch Accrual and Randomization Diagram

Study duration

We anticipate conducting chart review for two months, mailed outreach and reminder follow-up for two months, waiting for completion of screening for an additional four months, conducting the sub-sample survey for one month, and data analysis and manuscript compilation for 3 months. Thus, we anticipate this project to last 12 months. We anticipate screening ultrasounds to take approximately 1 hour. For the subsample of participants completing the follow-up survey, we would expect the phone call to take approximately 15 minutes.

Resources necessary for human research protection

[name] and [name] along with Project Manager [name] and Clinical Research Coordinator [name] are adequately informed of the protocol and adequately qualified to conduct research via training required for medical doctors/students and research coordinators. All are up to date with HIPAA and CITI training.

Characteristics of the Study Population

Target population

The study population includes patients with cirrhosis who receive care at any Penn Gastroenterology clinic and are overdue for HCC surveillance.

Subjects enrolled by Penn Researchers

600

Subjects enrolled by Collaborating Researchers

0

Accrual

Through automated data extraction from Clarity, we will identify potentially eligible patients. The research team will review the electronic medical record charts in EPIC to confirm study eligibility. Providers of eligible patients will be sent an email that allows them to opt out of participation on behalf of their patients. Patients who are eligible and whose providers do not opt out of the intervention will be randomized into one of the three arms of the intervention.

Based on preliminary review of the data, we anticipate approximately 860 screening eligible patients: 700 in the initial batch and 160 in the second batch. We know that roughly 30% of patients complete screening outside of Penn or will be ineligible based on chart review, leaving approximately 600 eligible patients.

Key inclusion criteria

Patients who are 18+ years old with a current diagnosis of cirrhosis or advanced fibrosis receiving care at any Penn Gastroenterology/Hepatology practice, who must have had 1 or more visits to a Penn Gastroenterology/Hepatology practice in the preceding two years and are currently followed by Penn GI, and who must live in the Philadelphia Metropolitan Statistical Area. All patients meeting these criteria will be included regardless of race, ethnicity, or gender.

Key exclusion criteria

Patients with a history of HCC or other liver carcinoma diagnosis, history of liver transplant, and/or have completed screening within the past 7 months, have a future screening scheduled, or a different screening modality (MRI, CT, etc.) recommended by their physician. We will also exclude patients with metastatic cancer or receiving hospice care.

Vulnerable Populations

No vulnerable populations are included in the research study.

Populations Vulnerable to Undue Influence or Coercion

We are not specifically targeting any vulnerable populations.

Subject Recruitment

Through automated data extraction from Clarity, we will identify potentially eligible patients. The research team will review the electronic medical record charts in EPIC to confirm study eligibility. Providers of eligible patients will be sent an EPIC inbox message that allows them to opt out of participation on behalf of their patients. Patients who are eligible and whose providers do not opt out of the intervention will be randomized into one of the three arms of the intervention. We will obtain a waiver of consent for this low-risk intervention as it would not be possible to assess response if we had to obtain consent prior to outreach.

Subject Compensation

Yes, subjects will be financially compensated for their participation.

One intervention arm will receive monetary compensation of a Greenphire ClinCard worth \$20. The other two study arms will not receive compensation.

Procedures

Screening – Once patients are confirmed as eligible, a list will be sent to each provider to opt-out of the study on the patient's behalf.

Randomization - Subjects will be randomly assigned Study ID numbers and then randomized in three batches in a 1:2:2 ratio to one of three arms using a computer-generated randomization algorithm stratified by batch. The research coordinator will record the randomization assignments on a master list which will be maintained by the research coordinator on a password protected computer. The research staff will assemble the mailings based on this master list. For the post-intervention phone interviews, a proportion of the 134 subjects will be randomly selected from each batch of randomized participants mailed outreach, based on batch size, using STATA. For example, if batch 1 contained 142 patients out of the total 480 randomized to one of the intervention arms, then 29.6% of the 134 subjects (equaling approximately 40) will be randomly selected from batch 1 to be called for the interview.

Intervention - Patients will either receive standard of care (usual care group), receive a letter encouraging them to get a surveillance ultrasound plus an order slip for the procedure (opt-out), or receive the letter and order slip plus an unconditional incentive of \$20 (incentive). Patients then have the option to complete the ultrasound. A second data pull will be used to determine ultrasound completion at 2 months after initial outreach for all patients in the study. If they have not completed screening within 2 months from initial outreach, the research staff will send a reminder similar to the original messaging and including the order slip. A reminder will not be sent if the patient has a future ultrasound scheduled or a different screening modality is now recommended. A final data pull will be used to determine ultrasound completion at 6 months from initial outreach for all patients in the study. Some patients may have their screening completed outside of Penn and View-only Care Everywhere encounters that have been downloaded into the patient's chart may be reviewed for this information. Care Everywhere will not be used to request clinical information for research purposes.

Sub-sample Questionnaire - A sub-sample of 134 patients will be called to complete a questionnaire over the phone 6 months after initial outreach was mailed. The subjects will confirm their eligibility (e.g. that they had received outreach about HCC surveillance) and be asked information about their qualitative experience with the outreach materials and approach. We anticipate these questionnaires to take no more than 15 minutes to complete over the phone. The research staff will make no more than three attempts to speak directly with the subject. Interviews will be recorded and transcribed.

Analysis Plan

1.1 Power and Sample Size

Approximately 860 potentially eligible subjects will be identified via a data abstraction by the Clarity database. Based on preliminary review, we estimate that 30% of patients complete screening outside of Penn or will not meet eligibility criteria per chart review, leaving approximately 600 eligible patients. As such, we anticipate we will have enough patients to enroll at least 600 subjects (and randomize in a 1:2:2 ratio to usual care, opt-out, and incentive arms). We estimate a base return rate for the usual care arm to be 10%. We will consider a meaningful increase in response rate to be 13 percentage points for the opt-

out arm as compared to usual care (23%), and 13 percentage points for the incentive arm as compared to the opt-out arm (36%). This will be sufficient sample size using a two-tailed chi-square test of proportions with 80% power and a Type 1 error rate of .025, accounting for two pairwise comparisons with Bonferroni correction (.05/2 = .025).

1.2 Data analysis

We will conduct a chi-squared test of proportions analysis using Stata to compare arm 2 to arm 1 and arm 3 to arm 2 separately using intent-to-treat protocol for the ultrasound completion and any HCC surveillance imaging completion. As exploratory analyses, we will evaluate response by age, gender, race/ethnicity, income at the level of zip code, etiology of cirrhosis, and provider/specialty. We will also evaluate differences in response rate among MyPennMedicine users and non-users and scheduling modality (MyPennMedicine vs. call). Additionally, we will evaluate the percentage of HCC surveillance images that are abnormal, result in follow-up imaging, result in a diagnosis of HCC and follow-up care, and incidental findings during imaging between the study arms. Analysis will be conducted at least six months after initial outreach.

Qualitative analysis of the post-intervention phone interviews will be conducted using NVivo. This will include thematic analysis of patient experience with the intervention and screening process.

Analysis will be conducted by blinded members of the research team at least 6 months after the mailings have been sent.

Data Confidentiality

Paper-based records will be kept in a secure location and only be accessible to personnel involved in the study. Computer-based files will only be made available to personnel involved in the study through the use of access privileges and passwords. Wherever feasible, identifiers will be removed from study-related information. Audio and/or video recordings will be transcribed and then destroyed to eliminate audible identification of subjects.

Subject Confidentiality

Information about study subjects will be kept confidential and managed according to the requirements of the Health Insurance Portability and Accountability Act of 1996 (HIPAA). All PHI will be maintained on UPHS servers. Source documents are maintained in PennChart. No source documents will be printed or maintained in paper form at the study site. Data from PennChart will be recorded in Penn Medicine's REDCap system. The investigator and study team (which includes the research coordinator, and research assistants) will have access to PHI within PennChart and REDCap. We will label all PHI within REDCap as identifiable information so that de-identified exports are possible. All reports that include identifiable information will be stored on the Innovation Center secure drive, maintained behind the UPHS firewall. Direct identifiers will be maintained on RedCap until manuscript publication in case additional chart review is needed for confirmation of results. Once data analysis and manuscripts have been published, direct identifiers will be deleted from RedCap and the de-identified database will be stored on the Innovation Center secure drive. Phone calls will be transcribed using Datagain Transcription, a HIPAA compliant transcription service. Datagain's system controls, database architecture and internal policies provide HIPAA compliance.

Sensitive Research Information

This Research does not involve collection of sensitive information about the subjects that should be excluded from the electronic medical record.

Subject Privacy

Because this study involves sending a letter to patients which will include PHI such as name, etc., research staff will be required to check the address listed for the patient a second time after writing out the envelope to ensure it is not sent to the wrong address/wrong person. Research staff will also be required to check that the documents are addressed to the correct person prior to sealing the envelope. We will only interact with the subsample of subjects with which we plan to call to conduct a follow-up questionnaire. With these subjects, we will conduct phone calls in a private area. When we call subjects, we will confirm the identify before administering the questionnaire. We will not be interacting with subjects in person.

Data Disclosure

Greenphire ClinCard and the Office of Finance at the University of Pennsylvania will receive participant name, address, and date of birth for subject compensation payments. Completed surveillance ultrasound results will be disclosed to the participant's provider for continuity of care.

Protected Health Information/Data Protection

- Name
- Street address, city, county, precinct, zip code, and equivalent geocodes
- All elements of dates (except year) for dates directly related to an individual and all ages over 89
- Telephone and fax numbers
- Medical record numbers
- Biometric identifiers, incl. finger and voice prints

Consent Process

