1.3 Secondary outcome variable(s)

The secondary outcome is the proportion of subjects who have any hepatocellular carcinoma surveillance in the six-month period after the study begins.

Additional variables include the etiology of cirrhosis, demographic and socioeconomic characteristics of subjects who participate, differences by provider/specialty, number of clinic visits, differences among MyPennMedicine users and non-users, as well as exploratory qualitative data regarding experience with outreach. Additionally, we will track the percentage of HCC surveillance images that are abnormal, result in follow-up imaging, result in a diagnosis of HCC and follow-up care, and incidental findings during imaging.

Background

There is a substantial burden of HCC-related morbidity and mortality: The age-adjusted incidence rates of HCC have tripled in the US since the 1980s due to the burden of hepatitis C virus (HCV) and the epidemic of non-alcoholic fatty liver disease (NAFLD). The overwhelming majority of HCC in the US occurs in the setting of cirrhosis. The age group most affected by cirrhosis and HCC are baby boomers given that HCV is the leading risk factor for cirrhosis and HCC, followed by NAFLD, hepatitis B virus, and alcohol. The current burden of HCC translates to more than 30,000 new HCC diagnoses every year, with greater than 20,000 HCC-related deaths annually. The incidence of HCC is projected to increase over the next 10-20 years.

Early diagnosis of HCC dictates survival: The American Association for the Study of Liver Diseases (AASLD) recommends biannual HCC surveillance for all patients with cirrhosis using an abdominal ultrasound. These guidelines seek to maximize early diagnosis of HCC which leads to earlier detection and improved survival because early-stage HCC is curable, with 70% 5-year survival compared to 5% in advanced disease.

HCC surveillance rates are suboptimal: Despite longstanding published guidelines for HCC surveillance, adherence is low, with surveillance rates ranging from 15-30% in the US. Two RCTs have tested interventions to increase HCC surveillance, including electronic reminders for primary care providers and mailed reminders (with or without navigators), but neither has been scalable, produced durable responses, or increased surveillance rates above 50%.

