1.4 Additional Information to Subjects

Subjects will be sent a letter explaining that we are offering a special program to patients overdue for ultrasound. Subjects will receive information about the risks and benefits of surveillance ultrasound for HCC screening. Providers will disclose screening results directly to patients if completed.

Potential Study Risks

The risks associated with this study are no more than minimal. Loss of confidentiality is possible, but unlikely. We will minimize this risk by using de-identified information whenever possible and by maintaining all identifiable information on a secure drive and/or in a HIPAA-compliant system (e.g. REDCap). There is also the risk of psychological harm associated with being screened for cancer. This risk will be minimized by the timely communication of screening test results to the subject and the facilitation of follow up diagnostic testing as needed (as is usual practice for screening outreach programs).

Potential Study Benefits

If a participant completes HCC surveillance screening, which is standard of clinical care, the subjects will potentially benefit from participation by increasing the chances of identifying hepatocellular carcinoma at an early stage. Information from this study may benefit society through a better understanding of how to effectively increase overall participation rates in HCC surveillance according to guidelines.

Data and Safety Monitoring

Safety will be monitored on an ongoing basis by the PI and the study team. The PI or designee will review the study charts to evaluate events at each subject interaction to ensure the grade, relationship to the study procedure, expectedness and the course of action for each subject is documented. We will also participate in a Data Safety and Monitoring Board through NIH and the Penn/CHIBE Roybal pilot program.

Risk / Benefit Assessment

The risks associated with this study are no more than minimal. Better knowledge of how to increase mailed screening could potentially address one of the major barriers of accessing care, i.e. having patients come in for clinical office visits. The Principal Investigator believes that the risks of participating in the study are outweighed by the potential benefits of participating in the study.

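### Abnormality and HCC-diagnosis percentages are compared between arms among images done, a group the intervention itself changes, so the comparison is not a randomized one

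*Combined protocol and SAP*

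**What the plan says.** The sentence appears in section 1.2 Data analysis under Statistical Considerations and again under Analysis Plan: "we will evaluate the percentage of HCC surveillance images that are abnormal, result in follow-up imaging, result in a diagnosis of HCC". The list ends "and incidental findings during imaging between the study arms", which most naturally makes the whole list a between-arm comparison. Objectives 1.3 names the same measures among its additional variables, on the same denominator: "we will track the percentage of HCC surveillance images that are abnormal".

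The chi-square comparisons are specified "using intent-to-treat protocol for the ultrasound completion and any HCC surveillance imaging completion". Intent-to-treat is stated for nothing else. The documents name no yield per randomized patient, give no caveat on reading the per-image percentages across arms, and have no rule for a patient with more than one image.

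**The concern.** The Intervention paragraph under Procedures leaves completion of the ultrasound to the patient, after allocation. The power section plans for that choice to differ by arm. Restricting a comparison to those imaged therefore conditions on the trial's own outcome. Patients who would be imaged without a letter and patients imaged because of it may carry different risk, and randomization does not balance that mix.

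The per-image percentage properly describes the people imaged. It does not show whether outreach finds more disease per patient offered it. That question is close at hand, because Potential Study Benefits describes the gain to those who complete screening as "increasing the chances of identifying hepatocellular carcinoma at an early stage". A reader who took a lower per-image percentage in the outreach arms as an effect of outreach could conclude that it lowers yield when it finds more cases.

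**Working it through.** **The plan's own figure.** No figure is stated for the yield comparison. The stated 80% power for the completion comparisons (two-sided alpha 0.025) was reproduced first, to confirm the inputs, with

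z = (|p2 − p1| − 2.241·√[p̄(1 − p̄)(1/n1 + 1/n2)]) / √[p1(1 − p1)/n1 + p2(1 − p2)/n2].

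- 10% vs 23%, 120 vs 240 patients: power 79.9%.
- 23% vs 36%, 240 vs 240 patients: power 81.3%.

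**Inputs.** Arm sizes 120, 240 and 240 come from Study Design 1.1. Uptake of 10%, 23% and 36% comes from Power and Sample Size.

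Assumptions that are not in the documents:
- One image per patient.
- The uptake figures apply to any surveillance image.
- The same 10% would be imaged anyway in every arm.
- The abnormality rates used below.

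**Imaged patients.**
- Usual care: 120 × 0.10 = 12.
- Opt-out: 240 × 0.23 = 55.2, of whom 24 would be imaged anyway and 31.2 are extra.
- Incentive: 240 × 0.36 = 86.4, of whom 24 would be imaged anyway and 62.4 are extra.

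**Formulas.** Let u be uptake without outreach, d the added uptake, r0 the abnormality rate in those imaged anyway and r1 the rate in the extra patients.

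- Per randomized patient: u·r0 + d·r1.
- Per image: (u·r0 + d·r1)/(u + d).
- Per-image difference from usual care: d(r1 − r0)/(u + d).

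The last line is the key result. The sign of the per-image difference depends only on whether the extra patients are at higher or lower risk than those imaged anyway. It says nothing about whether more abnormalities are found.

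**Results** (usual care / opt-out / incentive):

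| r0 / r1 | Abnormal patients | Per image, % | Per randomized, % |
|---|---|---|---|
| 25% / 10% | 3 / 9.12 / 12.24 | 25.0 / 16.5 / 14.2 | 2.5 / 3.8 / 5.1 |
| 10% / 10% | 1.2 / 5.52 / 8.64 | 10.0 / 10.0 / 10.0 | 1.0 / 2.3 / 3.6 |
| 10% / 20% | 1.2 / 8.64 / 14.88 | 10.0 / 15.7 / 17.2 | 1.0 / 3.6 / 6.2 |

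Step changes in percentage points (opt-out minus usual care, then incentive minus opt-out):

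- Per randomized: +1.3 and +1.3; +1.3 and +1.3; +2.6 and +2.6.
- Per image: −8.5 and −2.4; 0 and 0; +5.7 and +1.6.

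**A second model gives the same pattern.** Assume 20% of patients are high-risk, with abnormality rates of 40% (high-risk) and 10% (low-risk). Usual-care uptake is 30% and 5% respectively, and outreach adds 13 or 26 points in both groups. Per image the figures are 28.0 / 21.2 / 19.3%. Per randomized patient they are 2.8 / 4.9 / 7.0%.

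**Precision.** With about 12 images in usual care, 3 of 12 abnormal has an exact 95% interval of about 5% to 57%. On the randomized denominator, 3 of 120 has an exact interval of 0.5% to 7.1%.

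**The case against.** The strongest reply is that the plan never claims these percentages measure an effect of outreach. They are additional variables to be tracked and evaluated, with no hypothesis, test or alpha. The aims concern participation, and the chi-square tests under intent-to-treat are kept for the two completion outcomes. The stated benefit is also conditional on completing screening, so the document promises no yield per patient offered outreach. All of this stands, and it keeps the point minor.

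Three further points are fair:
- The abnormality rates are assumed, and the rise per randomized patient follows by construction whenever the extra patients have any abnormality. The scenarios show that the two measures can diverge. They do not predict that they will in this trial.
- The power section speaks of return and response rates without saying whether these mean ultrasound only. If other imaging counts as well, the imaged numbers would be larger than 12, 55 and 86.
- With one image per patient, a reader could rebuild the per-randomized yield as completion times the per-image percentage, for example 10% × 25% = 2.5%.

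None of this removes the problem. The text compares image-based percentages between arms, and an untested comparison on a denominator the intervention shifts can still be misread. The word exploratory is attached to the preceding subgroup sentence. Carrying it over to this one is a fair reading, but the plan does not say so.

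**Conclusion.** The concern holds, as a minor one. The per-image between-arm contrast conditions on a post-randomization event planned to differ at 10%, 23% and 36%, and the plan offers no per-randomized counterpart. In the three assumed scenarios the per-image step ranges from −8.5 to +5.7 points while the per-randomized step is always positive, at 1.3 to 2.6 points. The direction and size in this trial cannot be derived from the documents, because they depend on the unknown risk of the extra patients imaged. The structural point does not depend on those assumed rates. The primary and secondary completion analyses are unaffected.

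**What to change.** In both data-analysis sections, define the between-arm comparison as the proportion of all randomized patients with at least one abnormal surveillance image, follow-up imaging, HCC diagnosis or incidental finding. Report risk differences for opt-out versus usual care and incentive versus opt-out, with confidence intervals, and label them exploratory. Keep the per-image percentages by arm as description only, with no between-arm test, and state whether the unit is the image or the patient.

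The cost is SAP wording. The events are already to be tracked under Objectives 1.3, and the randomized denominators are known. The drawback is imprecision: across the three scenarios, power for the two pairwise contrasts is about 8% to 26% at two-sided 0.05, so the intervals will be wide relative to the differences. The per-randomized figure also measures detection through imaging, not how common the disease is, and should be described that way.
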